13.6. Sub-group Analyses

The primary efficacy endpoint (OS) and secondary efficacy endpoint (EFS) will be analyzed for each sub-group defined according to the following:

- Age (<60, and ≥ 60 years)
- Age (<65 years, ≥ 65 to <75 years, and ≥ 75 years)
- Sex at birth (male, and female)

- Race (White, Black or African American, Asian, and Other)
- Ethnicity (Hispanic or Latino, Non-Hispanic or Latino)
- Geographical region (North America, Europe and Australia, and Rest of World)
- Stratification factors from randomization (response to prior therapy and pre-selected salvage therapy, separately)
- FLT3-ITD allelic burden (using central testing) at randomization >50%, >25% to ≤50%, and ≤25%)
- De novo AML and secondary AML
- Prior allogeneic HSCT (yes and no)
- AML cytogenetic risk score (favorable, intermediate, unfavorable, and unknown risk)
- Blast count at baseline (less than median and greater than or equal to median)

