3.3. Clinical Studies

A brief summary is given below. Refer to the current quizartinib [Investigator's Brochure](#) for additional information on clinical experience with quizartinib.

As of 22 Jan 2016, a total of 1289 subjects received quizartinib in 19 clinical studies including 624 subjects with either AML or solid tumors, 472 healthy volunteers, and 193 subjects with AML, ALL and MDS in 4 investigator sponsored trials.

Quizartinib was studied in 76 AML subjects in a Phase 1 study with intermittent dosing (14 days on drug followed by 14 days rest) from 12 mg to 450 mg, and continuous dosing at 200 mg and 300 mg.⁸ Plasma taken from subjects and assayed in an in vitro plasma inhibitory assay, showed maximal inhibition of FLT3-ITD signaling at 60 mg dose as early as 2 hours after the first dose. A marked reduction of FLT3-ITD phosphorylation in vivo was also observed at 60 mg and

higher doses. The overall response rate was 53% in FLT3-ITD(+) subjects and 14% in FLT3-ITD(-) subjects.

The response rate observed in Phase 1 was confirmed in the Phase 2, AC220-002 study of single agent quizartinib in relapsed or refractory AML. In this Phase 2 study a total of 333 subjects were enrolled in 2 cohorts; Cohort 1 included subjects 60 years or older who were relapsed or refractory to 1 line of therapy and Cohort 2 included subjects 18 years or older who were relapsed or refractory to salvage therapy or relapsed after HSCT. In Cohort 1, the CRc rate was 57% in FLT3-ITD(+) subjects with a median survival of 25.3 weeks.⁴ Cohort 2 showed a CRc rate of 46% in FLT3-ITD(+) subjects with a median survival of 24.0 weeks.⁵ Importantly, 35% of Cohort 2 FLT3-ITD(+) subjects were bridged to HSCT. Almost all (94%) subjects proceeding to HSCT had achieved a CRc or partial remission (PR) on quizartinib and their 1 year survival rate was 39%.

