5.2.2. Selection of $\geq 3\%$ FLT3-ITD Allelic Ratio as Cutoff for Study Eligibility

In previous Phase 2 studies with quizartinib, subjects with an allelic ratio of FLT3-ITD to total FLT3 of $> 10\%$ were defined as ITD(+), however, for the Phase 3 study the cutoff will be reduced to $\geq 3\%$ based on the limit of quantitation for the clinical diagnostic assay. The lower ITD ratio for eligibility will allow those subjects with a reliably detectable and quantifiable ITD mutation to be enrolled and to determine the potential benefit from quizartinib. Analysis of “ITD(-)” subjects from the AC220-002 Study showed that those subjects with a low level ($\leq 10\%$) of the ITD mutation had similar response rates to positive ($> 10\%$) subjects, while those with no detectable ITD mutation ($< 0.3\%$) had lower response rates.

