5.4. Selection of Study Population

5.4.1. Inclusion Criteria

To be able to participate in this study, candidates must meet the following criteria at screening or other specified time point:

1. Provision of written informed consent approved by the Institutional Review Board (IRB) or Independent Ethics Committee (IEC) with privacy language in accordance with national regulations (eg, HIPAA authorization for US sites) prior to any study-related procedures, including withdrawal of prohibited medications if applicable.
2. Age ≥ 18 years or the minimum legal adult age (whichever is greater) at the time of informed consent.
3. Morphologically documented primary AML or AML secondary to myelodysplastic syndrome (MDS), as defined by World Health Organization criteria, as determined by pathology review at the study site.
4. In first relapse (with duration of remission of 6 months or less) or refractory after prior therapy, with or without HSCT. Induction therapy must have included at least 1 cycle of an anthracycline/mitoxantrone-containing induction block at a standard dose.
 - Refractory is defined as:
 - After 1 cycle, a reduction in bone marrow blasts of less than 50% and failure to achieve a CR, CRp, or CRi.
 - After 2 cycles, lack of achievement of CR, CRp, or CRi.
 - First relapse (with duration of remission of 6 months or less) is defined as:
 - Achievement of CR, CRi, or CRp, as defined by 2003 International Working Group criteria (Section 7.2) after initial AML therapy with or without consolidation or maintenance, and with or without HSCT.
 - Duration of CR, CRi or CRp is measured from the date of the bone marrow assessment which confirmed response or the date of allogeneic transplantation, to the date of the bone marrow assessment that identified relapse or the appearance of peripheral blasts.
5. Presence of the FLT3-ITD activating mutation in bone marrow or peripheral blood (allelic ratio as determined by a central laboratory with a cutoff of $\geq 3\%$ FLT3-ITD/total FLT3). If a specimen has been sent for FLT3-ITD testing at the central laboratory but the subject requires treatment for AML before the central FLT3-ITD test result is available, a local test result may be acceptable for randomization after consultation with the Medical Monitor.

6. Eligibility for pre-selected salvage chemotherapy, according to the Investigator's assessment.
7. ECOG performance score 0-2.

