6.2. Study Visits

6.2.1. Screening Activities

Eligible subjects will be screened as outlined below. Unless otherwise specified, screening procedures must be completed within 14 days prior to randomization to determine that subjects meet inclusion criteria and do not meet exclusion criteria.

- Written informed consent
- Medical and disease history and demographics
- Physical examination
- Vital sign determinations
- ECOG performance status evaluation
- Assessment of prior and concomitant medications, including medications received within 28 days prior to screening.
- Pregnancy testing; women of childbearing potential must have a negative serum (minimum sensitivity 25 IU/L or equivalent units of hCG).
- Determination of coagulation profile (prothrombin time [PT]/international normalized ratio [INR])
- Chest X-rays (posterior/anterior and lateral)
- 12-lead ECG (triplicate)
- Collection of samples for clinical laboratory tests (hematology, chemistry, and urinalysis)
- MUGA scan or ECHO to be performed at screening on all subjects unless a scan performed within 1 month of screening revealed LVEF \geq 45%.
- Bone marrow aspiration and biopsy for central confirmation of diagnosis; biopsy may be omitted if the aspirate is considered to be adequate. If a specimen has been sent for central testing but the subject requires treatment for AML before the central FLT3-ITD test result is available, a local test result may be acceptable for randomization after consultation with the Medical Monitor. A Screening specimen must be sent to the central laboratory for confirmation, and results compared to the local test result.

In cases where subjects have been randomized and the FLT3-ITD local and central laboratory results are discordant the subjects may continue with quizartinib dosing.

- Collection of bone marrow specimen and whole blood (at approximately the same time) for FLT3-ITD testing (and other AML associated mutations) by central laboratory. If it is not feasible to obtain a bone marrow specimen at Screening, peripheral blood only may be submitted to Navigate BioPharma Services, Inc, a Novartis Company (Navigate).

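### The lowest central allelic-burden subgroup (≤25%) has no 3% floor, so subjects admitted on a local test with a central ratio below 3% would be analysed as low-burden FLT3-ITD(+)

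*Combined protocol and SAP*

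**What the plan says.** - **Subgroup.** Section 13.6 lists, among the OS and EFS subgroups, "FLT3-ITD allelic burden (using central testing) at randomization >50%, >25% to ≤50%, and ≤25" per cent. It has no floor and no category for a negative, unquantifiable or missing central result. In the same list, cytogenetic risk does have an unknown category.
- **Eligibility.** Inclusion criterion 5 (Section 5.4.1) requires an "allelic ratio as determined by a central laboratory with a cutoff of" ≥3%. The same criterion adds that, when treatment cannot wait for the central result, "a local test result may be acceptable for randomization after consultation with the Medical Monitor".
- **Discordance.** Section 6.2.1 requires a screening specimen to go to the central laboratory and the two results to be compared. It then says: "In cases where subjects have been randomized and the FLT3-ITD local and central laboratory results are discordant the subjects may continue with quizartinib dosing". It gives no analysis rule for these subjects.
- **Analysis sets.** Under Section 13.4 the ITT set is all randomized subjects. The per protocol set drops subjects with major deviations.
- **Earlier data.** Section 5.2.2 reports that, in the Phase 2 study AC220-002, subjects with a low ITD level (≤10%) responded about as often as those above 10%. Subjects with no detectable ITD (<0.3%) responded less often.

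**The concern.** A reader of the subgroup table will take the ≤25% row as the treatment effect in subjects who carry the mutation at low burden. As written, the row can also hold subjects in whom the central assay found no ITD, or ITD below the eligibility cutoff, and who entered on a local result. If quizartinib does less for subjects without detectable ITD, their presence moves this row, and only this row, toward a hazard ratio of 1. The table could then show benefit falling off at low burden when the cause is misclassified ITD status.

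The objectives are stated for FLT3-ITD(+) AML, yet the only OS sensitivity analysis that Section 13.4 names is censoring at HSCT. No analysis in centrally confirmed subjects is named.

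**Working it through.** **The plan's own figures, for context.** The design hazard ratio is 3.9/6 = 0.65. With 2:1 allocation, a Lan-DeMets O'Brien-Fleming boundary at half the information and a futility stop at 10% conditional power under the current trend, 280 deaths give 90.0% power, which matches Section 13.3. This point disputes neither figure.

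**Step 1: where a central ratio of 0 to <3% goes.** Criterion 5 can admit the subject on a local test. Section 6.2.1 does not remove the subject after a discordant central result. ITT keeps everyone randomized. Section 13.6 classifies by the central value, and any value from 0 to <3% satisfies ≤25%.

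**Step 2: whether another planned analysis removes them.** Section 14.7 gives randomizing a subject who fails the entry criteria as an example of a deviation. But criterion 5 itself allows local-test entry, so a local-positive, central-negative subject is arguably compliant. The per protocol analysis therefore does not clearly exclude these subjects.

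**Step 3: size, for illustration only.** Neither the discordance rate nor the ratio distribution is in the documents. Assume a true hazard ratio of 0.65 in ITD(+) subjects, 1.0 in ITD-negative subjects, and a share p of the band that is negative. Averaging on the log scale (an approximation), the apparent hazard ratio is exp[(1 − p) × ln 0.65], with ln 0.65 = −0.431.

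| p | Apparent hazard ratio |
|---|---|
| 10% | exp(−0.388) = 0.68 |
| 20% | exp(−0.345) = 0.71 |
| 30% | exp(−0.302) = 0.74 |

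If the band held 30% of 363 subjects (109, also an assumption), p = 10-30% would mean about 11 to 33 subjects, or 3-9% of the trial.

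If half of the subjects below 3% benefited like ITD(+) subjects, p would in effect halve to 5-15%, and the apparent hazard ratio would be exp(−0.409) = 0.66 to exp(−0.366) = 0.69.

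**Step 4: set against the band's precision.** A band with 30% of subjects would have about 0.30 × 280 = 84 deaths. The standard error of the log hazard ratio is 1/√(84 × 2/9) = 0.23, so the 95% interval around 0.65 is about 0.41-1.02. A move to 0.68-0.74 is 0.043-0.129 on the log scale, or about 0.2-0.6 standard errors.

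**The case against.** **The pooling is inferred.** Section 13.6 does not say whether a not-detected or missing central result counts as a burden of 0 or is left unclassified. That is correct. Pooling is what the words give when taken literally; otherwise the rule is undefined. Either way it should be written down.

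**The Phase 1 response rates do not size the effect.** Section 3.3 states: "The overall response rate was 53% in FLT3-ITD(+) subjects and 14% in FLT3-ITD(-) subjects". A reader might use this contrast to measure the dilution. It comes from a study across a wide dose range with 17 FLT3-ITD(+) subjects (Section 5.2.3), and single-arm response rates do not give a survival hazard ratio. Section 5.2.2 is closer to the question, and it reports lower response only where ITD was undetectable. Because 3% is the assay's quantitation limit, some subjects below it may carry the mutation and benefit. This weakens the assumed hazard ratio of 1.0 and shrinks the shift, but does not reverse it.

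**Section 5.2.2 does not promise an analysis of the 3-10% group.** It says the lower cutoff allows subjects with measurable ITD "to be enrolled and to determine the potential benefit from quizartinib". A reader might infer a planned estimate in the newly admitted range, but no objective in Section 4 asks for one. Nor is the group beyond reach, since the ratio is a recorded variable (Section 5.7.6).

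**The companion diagnostic is not tied to this band.** Section 6.2.1 says that the test results will support its development, and mentions neither the 3% cutoff nor the ≤25% subgroup in that connection.

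**Local entry is an exception, and the shift is small against sampling error.** Both are true, and they limit the importance of the point. They do not justify a band that mixes eligible and centrally ineligible ratios.

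**A missing sensitivity analysis is not proof of omission.** Section 13.4 defers the detail of sensitivity analyses to the SAP, and the combined document as available holds no separate SAP text on these categories. If such text exists, the protocol should point to it.

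**Conclusion.** The point holds as a defect in a subgroup definition. As written, the lowest burden band can include subjects with a central ratio of 0 to <3%, and their presence would tend to move its hazard ratio toward 1. The illustrative range of 0.68-0.74 for a true 0.65 rests on an assumed 10-30% negative share, an assumed hazard ratio of 1.0 in those subjects, and log-scale averaging. The actual size cannot be derived from the documents.

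A reader might infer that the trial's main result is at risk. It is not: the primary ITT test does not use these bands, and the subgroups carry no alpha. The comparison within the band also remains randomized, because the central specimen is taken at screening. What is unclear is which population the estimate describes.

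**What to change.** 1. In Section 13.6, change the lowest band from ≤25% to ≥3% to ≤25%.
2. In the same place, report central <3%/not detected and central result missing as two separate categories, outside the burden bands.
3. In Section 13.4, add one OS sensitivity analysis restricted to subjects with a central ratio ≥3%. Keep ITT as primary.

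A further descriptive split at 10% is optional. If 10% of subjects lay at 3-10% (an assumption), that group would have about 36 subjects and 28 deaths, with a 95% interval of about 0.30-1.43 around 0.65.

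The cost is a wording change and one extra analysis. Section 6.2.1 already requires the central specimen, so no new data are needed. The separate categories may be small with wide intervals. The wording should be settled before treatment-group survival results are seen. None of this bears on the dosing rule for discordant subjects.

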13.7. Additional Efficacy Analyses

Statistical analyses of exploratory efficacy endpoints include:

- Kaplan-Meier analysis of duration of CRc and CR
- Cochran-Mantel-Haenszel (CMH) test of CR rate
- CMH test of CRc rate
- CMH test of transplantation rate

13.8. Safety Analysis

The safety analysis set (SAF) includes all subjects receiving at least 1 dose of study treatment (quizartinib or salvage chemotherapy).

Safety evaluation will be based mainly on AEs, clinical laboratory test results, physical examination results, vital signs, ECG results and ECOG performance scores. Descriptive statistics will be used to summarize safety data. All safety data will be summarized by treatment.

All summaries of AEs will include only treatment-emergent events unless otherwise stated. Adverse events will be categorized by system organ class and preferred term using the most current MedDRA dictionary, and will be graded according to NCI CTCAE v4.03.

Additional safety analysis for subjects in post-HSCT quizartinib arm may be performed.

The safety data will also be summarized for each sub-group defined according to the following:

- Age (< 60 and ≥60 years)
- Age (<65, ≥65 to <75, and ≥75 years)
- Sex at birth (male and female)
- Race (Caucasian, Black or African American, Asian, and Other)
- Ethnicity (Hispanic or Latino, Non-Hispanic or Latino)

- Concomitant use of strong CYP3A4 inhibitor (yes and no)
- Baseline ECOG performance score (0, 1, ≥ 2)
- Baseline body mass index (<18.5, 18.5 to <25, 25 to <30, ≥ 30 kg/m²)
- Prior allogeneic HSCT (yes and no)

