Safety evaluation will be based mainly on AEs, clinical laboratory test results, physical examination results, vital signs, ECG results and ECOG performance scores. Descriptive statistics will be used to summarize safety data. All safety data will be summarized by treatment (quizartinib or salvage chemotherapy). The safety data will also be summarized for pre-defined sub-groups.

All summaries of AEs will include only treatment-emergent events unless otherwise stated. Adverse events will be categorized by system organ class and preferred term using the MedDRA dictionary (version 14.1), and will be graded according to NCI CTCAE v4.03.

Additional safety analysis for subjects in post-HSCT quizartinib arm may be performed.

Additional Analyses

AML mutations, pharmacogenomic, pharmacoproteomic, and pharmaco-economic analyses will be performed.

Interim Analysis

The study design provides for one formal interim analysis when 50% (140) of the final number of events have been observed. At the discretion of the DMC, one of the following actions will occur at this interim analysis:

- Termination of the study for futility
- Termination of the study for efficacy
- Continuing the study as planned

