5.1.2. Treatment

A flow chart of study activities is presented in [Figure 1](#).

For subjects randomized to quizartinib the starting dose will be 30 mg/day unless the subject is receiving concurrent therapy with a strong CYP3A4 inhibitor, in which case the starting dose will be 20 mg/day. The dose will be taken in the morning with or without food over continuous 28-day cycles. If the subject omits taking quizartinib in the morning, it may be taken later in the day (until midnight), otherwise the dose should be considered missed. If the subject vomits after

taking quizartinib, no replacement dose should be given. Detailed information on quizartinib dosing is provided in Section 5.6.4.1.

The dose of quizartinib will be increased at Day 16 or Cycle 2 Day 1 according to the criteria specified in Section 5.6.4.3. Following dose escalation, triplicate ECG determinations should be performed at least once weekly for 2 weeks to monitor QTcF prolongation.

If necessary, the dose of quizartinib may be reduced according to the criteria described in Section 5.6.4.4.

See also Section 8.5 for details of QTcF management when prolongation is observed.

[figure not shown]
In subjects receiving quizartinib or LoDAC, treatment should continue until there is no longer clinical benefit from therapy, or until unacceptable toxicity occurs. For subjects receiving LoDAC the initiation of cycles may be delayed for up to 14 days to allow for recovery from toxicity.

Subjects that receive either quizartinib or LoDAC will be assessed for response on Day 1 of Cycle 2 and Day 1 of Cycle 3 as well as on Day 1 of each subsequent cycle unless the subject has already achieved CR, CRp, or CRi. In that event, bone marrow testing will be repeated after every 3 subsequent cycles, unless there is evidence of relapse.

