5.6.2. Method of Assigning Subjects to Treatment Groups

Upon providing written informed consent and initiation of screening procedures, a unique number will be assigned to each subject. Subjects will maintain this number throughout the study.

Subjects will be randomized into the two treatment groups in a 2:1 ratio (242 quizartinib and 121 salvage chemotherapy) and the randomization will be stratified by prior therapy and response, and pre-selected salvage chemotherapy:

Prior therapy and response:

- Relapsed in ≤ 6 months (not post HSCT)
- Refractory
- Relapsed in ≤ 6 months post allogeneic HSCT

Pre-selected chemotherapy, even for subjects subsequently randomized to quizartinib:

- High intensity chemotherapy (MEC; FLAG-IDA)
- Low intensity chemotherapy (LoDAC)

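### Safety is tabulated against one pooled chemotherapy column, and the safety subgroups omit pre-selected intensity, a randomization stratum, so an excess of toxicity over LoDAC can be hidden

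*Combined protocol and SAP*

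**What the plan says.** Section 13.8 says "All safety data will be summarized by treatment". On its own, the word treatment could be read as regimen. The Safety Analyses paragraph of the synopsis settles it: "All safety data will be summarized by treatment (quizartinib or salvage chemotherapy"). There are therefore two columns.

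Section 13.8 continues: "The safety data will also be summarized for each sub-group defined according to the following". Nine groupings follow: age (two sets of cut-points), sex, race, ethnicity, concomitant strong CYP3A4 inhibitor, baseline ECOG score, baseline body mass index and prior allogeneic HSCT. Pre-selected chemotherapy is not among them. The synopsis and Section 8 mention pre-defined subgroups for safety without naming any. The only other safety analysis named is an optional one for post-HSCT quizartinib subjects.

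Section 5.6.2 makes intensity a randomization stratum, with MEC and FLAG-IDA as high intensity and LoDAC as low. It is recorded in both arms: "Pre-selected chemotherapy, even for subjects subsequently randomized to quizartinib". For OS and EFS, Section 13.6 lists as a subgroup "Stratification factors from randomization (response to prior therapy and pre-selected salvage therapy, separately").

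**The concern.** The control column combines subcutaneous low-dose cytarabine with two intensive intravenous combinations (Section 5.6.4.2). Its event rate is a weighted mean of unlike regimens, with weights set by what investigators happened to pre-select. If the intensive regimens are more toxic and predominate, quizartinib can look no worse than control overall and yet be worse than LoDAC for the subjects who would otherwise have received LoDAC.

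Efficacy will be shown within each intensity stratum and safety, on the stated list, will not. A reader could then not weigh benefit against harm stratum by stratum. Safety also enters a decision: under Section 13.10 the DMC considers safety and benefit-risk if conditional power crosses the 10% futility boundary.

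Exposure adds to the problem. Section 5.1.2 says: "In subjects receiving quizartinib or LoDAC, treatment should continue until there is no longer clinical benefit from therapy, or until unacceptable toxicity occurs". MEC and FLAG-IDA stop after at most two cycles (notes to Table 5), and adverse events are collected until 30 days after the last dose (Section 8). The pooled column therefore mixes different periods at risk as well as different toxicities.

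**Working it through.** **The plan's own figure.** The plan gives no safety figure to reproduce. Its only formal sizing figure is 280 deaths for 90% power on OS (Section 13.3). With a Lan-DeMets O'Brien-Fleming boundary at half information and stopping for conditional power below 10% under the current trend, 280 deaths at a hazard ratio of 0.65 and 2:1 allocation give 90.0%. Nothing below touches it.

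**Inputs.** From the plan: 242 and 121 subjects, 2:1 allocation, stratified by intensity. Assumed, because the documents give neither: the LoDAC share f, and the event rates pH (MEC/FLAG-IDA), pL (LoDAC) and pQ (quizartinib, taken as equal in both strata).

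**Pooled control rate.** pC = f × pL + (1 − f) × pH. With pH = 45%, pL = 15%, pQ = 30%:

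| LoDAC share f | Pooled control rate | Pooled ratio (quizartinib/control) | Ratio in LoDAC stratum | Ratio in high-intensity stratum |
|---|---|---|---|---|
| 20% | 0.2×15 + 0.8×45 = 39.0% | 30/39.0 = 0.77 | 30/15 = 2.0 | 30/45 = 0.67 |
| 25% | 0.25×15 + 0.75×45 = 37.5% | 0.80 | 2.0 | 0.67 |
| 30% | 0.3×15 + 0.7×45 = 36.0% | 0.83 | 2.0 | 0.67 |
| 40% | 0.4×15 + 0.6×45 = 33.0% | 0.91 | 2.0 | 0.67 |
| 50% | 0.5×15 + 0.5×45 = 30.0% | 1.00 | 2.0 | 0.67 |
| 60% | 0.6×15 + 0.4×45 = 27.0% | 1.11 | 2.0 | 0.67 |

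**Where masking ends.** Setting pC = pQ gives f* = (pH − pQ)/(pH − pL). Here f* = (45 − 30)/(45 − 15) = 50%. Below it the pooled column favours quizartinib; above it the pooled column shows an excess. Other assumed rates move the crossing:

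- pH 40%, pL 15%, pQ 30%: f* = 10/25 = 40%
- pH 50%, pL 15%, pQ 30%: f* = 20/35 = 57%
- pH 75%, pL 40%, pQ 60%: f* = 15/35 = 43%

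**Precision in the LoDAC stratum.** The 95% half-width for the difference is 1.96 × √[pQ(1 − pQ)/nQ + pL(1 − pL)/nL], with nQ = 242f, nL = 121f, pQ = 30% and pL = 15%, taking all subjects as dosed:

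- f = 20%: about 48 v 24 subjects; 1.96 × √(0.21/48.4 + 0.1275/24.2) = 19 points
- f = 30%: about 73 v 36; 1.96 × √(0.21/72.6 + 0.1275/36.3) = 16 points
- f = 40%: about 97 v 48; 14 points
- f = 50%: about 121 v 60; 12 points

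The assumed excess over LoDAC is 15 points. At a 20–30% share the stratum table could show its direction and rough size but would not settle it.

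**The case against.** - **A tabulation may exist elsewhere.** Section 13.4 leaves the detail of the OS sensitivity analyses to a statistical analysis plan, and Section 13.8 does not say that its list is exclusive. This stands as a limit: the gap is in the stated list, and a by-intensity safety table elsewhere cannot be ruled out. If one exists, 13.8 should name it.
- **The pooled column matches the primary objective**, which compares quizartinib with salvage chemotherapy as a whole. This is right, and the pooled table should stay. It does not supply what 13.6 will show for efficacy.
- **The rates and the share are assumed.** They are. Masking needs intensive regimens that are both more toxic and predominant, and under the main illustration it disappears at a 50% LoDAC share. The point is that an excess can be hidden, not that it will be.
- **The LoDAC stratum may be small.** True, but safety is descriptive, and the plan already lists groups that may be small, such as age 75 or over.
- **QT prolongation, a known quizartinib risk, is covered separately** by central ECG reading, expedited reporting and concentration–QTc modelling (Sections 8.4, 8.5, 8.10 and 13.11). This narrows the concern to other toxicities.

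A reader might also infer that the within-stratum comparison is fully randomized. It is not quite. The safety set requires at least one dose, the trial is open-label (Section 5.6.5), and Section 6.2.6 provides for subjects who decline treatment before receiving any. The comparison is randomized apart from subjects never dosed.

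**Conclusion.** The concern holds as a reporting gap. On the stated plan, LoDAC is pooled with MEC and FLAG-IDA for safety, and the listed subgroups do not separate them, although the factor is a stratum known in both arms and is used for OS and EFS. Under the main illustration a doubling of risk relative to LoDAC appears as no excess or an apparent advantage at any LoDAC share up to 50%. Under the other assumed rates the crossing lies between 40% and 57%. These figures rest wholly on assumed rates and shares; the actual size cannot be established from the documents.

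Three stronger readings are tempting and not supported. The documents do not show that quizartinib is more toxic than LoDAC. They do not make the pooled table invalid; it is incomplete. Nor is information thrown away: the stratum is recorded for everyone, and what is missing is a pre-specified tabulation. Alpha, power, sample size and the primary analysis are unaffected.

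**What to change.** Add to the safety subgroups in Section 13.8: pre-selected salvage chemotherapy (high intensity: MEC/FLAG-IDA; low intensity: LoDAC), as randomized. Show the key tables (treatment-emergent events, Grade 3 or higher, serious events, discontinuations and deaths) within each stratum, beside the pooled column.

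Within a stratum, compare the quizartinib subjects pre-selected for that intensity with their own control. Setting all quizartinib subjects against LoDAC alone would lose the randomized comparison.

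State that the stratum tables are descriptive and that the LoDAC stratum may be imprecise. Note the unequal time on treatment when reading the high-intensity stratum, where open-ended quizartinib is set against at most two cycles; stratifying does not remove that difference.

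The cost is a line of wording and one extra set of tables. No new data, subjects or procedures are needed.
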